9.2 Evaluation during treatment

9.2.1 Patients will be evaluated weekly by the treating team during the escalation phase of metformin administration. Patients will be evaluated weekly by the radiation oncology team during concurrent chemoradiation as per current institutional protocol. The drug log will be reviewed on a weekly basis. Study staff may contact patients via telephone to discuss investigational drug compliance and/or any other study related questions or tasks. Additional visits will be obtained as clinically indicated. History and physical exams, along with appropriate laboratory studies (CBC, BMP) will be performed at each additional visit.

9.1.2 Sample collection for baseline correlative studies will be performed during treatment as outlined in the study calendar.

9.3 Evaluation following treatment

9.3.1 A brief history and physical examination by a medical, radiation or surgical (ENT or Head and Neck Surgery) oncologist, including laryngopharyngoscopy (mirror and/or fiberoptic and/or direct procedure), should be done at 10 weeks following completion of radiation then every 3 months through year 1 and every 4 months through year 2. A 30 day visit or telephone interview is required for evaluation of Adverse Events. Radiographic imaging (CT, MRI, or PET as appropriate) at these time points is highly recommended if disease progression is suspected by the treating physician. If performed, radiographic imaging to evaluate the patient for both local-regional recurrence and distant metastases is highly recommended.

- 9.3.2 Chest imaging: A chest CT or a PET/CT of chest is recommended once per year.
- 9.3.3 Biopsy of any lesion(s) suspicious for tumor recurrence is recommended as clinically indicated.
- 9.3.4 The initial post-radiation imaging evaluation (CT at 8-10weeks or PET-CT at 10-12weeks) after the completion of chemoradiation is recommended to assess disease response. The imaging can be contrast enhanced CT (neck and chest) or PET-CT of the head and neck or “whole body” PET/CT (minimum neck and chest) based on the preference of the treating clinician, but must be consistent with the pre-treatment imaging modality.

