9.2 Study Calendar

	Pre-study	wk -2 (d3+/-2d)	wk 1 (d3+/-2d)	wk 2 (d3+/-2d)	wk 3 (d3+/-2d)	wk 4 (d3+/-2d)	wk 5 (d3+/-2d)	wk 6 (d3+/-2d)	wk 7 (d3+/-2d)	30 days post radiation completion	Post-study (wk17+/-2wk)	Post-study (yr1 Q3mos)	Post-study (yr2 Q4mos)
Metformin tx		<-----BID metformin----->											
Chemo-radiation tx			<-----XRT (Daily); chemotherapy (weekly)----->										
Collected information (ONCORE)													
Metformin pill diary/compliance form		x	x	x	x	x	x	x	x				
Eligibility checklist	x												
Informed consent	x												
T, N, M staging	x												
Demographics	x												
Physical Exam	x	x	x	x	x	x	x	x	x		x	x	x
Medical history	x												
Vital signs	x										x	x	x
Weight	x	x	x	x	x	x	x	x	x		x	x	x
Performance status	x	x	x	x	x	x	x	x	x		x	x	x
Adverse event evaluation		x	x	x	x	x	x	x	x	x	x		
CMP	x												
CBC, BMP	x	x	x	x	x	x	x	x	x		x	x	x
Glucose monitoring (if applicable) (A)		x	x	x	x	x	x	x	x				
Disease response/radiologic evaluation											x	x	x
Pregnancy test	x (B)												
Imaging (C)	x										x	x	x
Laryngopharyngoscopy											x	x	x
pre-study items to be collected within 30 days of initiation of metformin treatment													
Pill diary/compliant may be discussed or completed via telephone.													
A: patients with hypoglycemia (<=60mg/dl) will receive instructions and supplies for BID glucose monitoring and recording													
B: Serum or urine pregnancy test (women of childbearing potential).													
C: Required within 8-12 weeks prior to registration, at end of radiation treatment, and at regular intervals following treatment completion.													
D= day, Wk= week, Mos= months, Yr= year; d3+/-2d= to be completed on day 3 of any given week, +/- 2days													

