Nephrotoxicity. Dose-related and cumulative renal insufficiency, including acute renal failure, is the major dose-limiting toxicity of cisplatin. Renal toxicity has been noted in 28% to 36% of patients treated with a single dose of 50 mg/m^2 . It is first noted during the second week after a dose and is manifested by elevations in BUN and creatinine, serum uric acid and/or a decrease in creatinine clearance. Renal toxicity becomes more prolonged and severe with repeated courses of the drug. Renal function must return to normal before another dose of cisplatin can be given. Elderly patients may be more susceptible to nephrotoxicity. Impairment of renal function has been associated with renal tubular damage. The administration of cisplatin using a 6-to 8-hour infusion with intravenous hydration, and mannitol has been used to reduce nephrotoxicity. However, renal toxicity still can occur after utilization of these procedures.

Ototoxicity. Ototoxicity has been observed in up to 31% of patients treated with a single dose of cisplatin 50 mg/m^2 , and is manifested by tinnitus and/or hearing loss in the high frequency range (4000 to 8000 Hz). The prevalence of hearing loss in children is particularly high and is estimated to be 40-60%. Decreased ability to hear normal conversational tones may occur. Deafness after the initial dose of cisplatin has been reported. Ototoxic effects may be more severe in children receiving cisplatin. Hearing loss can be unilateral or bilateral and tends to become more frequent and severe with repeated cisplatin doses. It is unclear whether cisplatin-induced ototoxicity is reversible. Vestibular toxicity has also been reported. Ototoxic effects may be related to the peak plasma concentration of cisplatin. Ototoxicity can occur during treatment or be delayed. Audiometric monitoring should be performed prior to initiation of therapy, prior to each subsequent dose, and for several years post therapy. The risk of ototoxicity may be increased by prior or simultaneous cranial irradiation, and may be more severe in patients less than 5 years of age, patients being treated with other ototoxic drugs (e.g. aminoglycosides and vancomycin), and in patients with renal impairment. Genetic factors (e.g. variants in the thiopurine S-methyltransferase [TPMT] gene) may contribute to cisplatin-induced ototoxicity; although this association has not been consistent across populations and study designs.

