Hematologic. Myelosuppression occurs in 25% to 30% of patients treated with cisplatin. The nadirs in circulating platelets and leukocytes occur between days 18 to 23 (range 7.5 to 45) with most patients recovering by day 39 (range 13 to 62). Leukopenia and thrombocytopenia are more pronounced at higher doses ($>50 \text{ mg/m}^2$). Anemia (decrease of 2 g hemoglobin/100 mL) occurs at approximately the

same frequency and with the same timing as leukopenia and thrombocytopenia. Fever and infection have also been reported in patients with neutropenia. Potential fatalities due to infection (secondary to myelosuppression) have been reported. Elderly patients may be more susceptible to myelosuppression. In addition to anemia secondary to myelosuppression, a Coombs' positive hemolytic anemia has been reported. In the presence of cisplatin hemolytic anemia, a further course of treatment may be accompanied by increased hemolysis and this risk should be weighed by the treating physician. The development of acute leukemia coincident with the use of cisplatin has been reported. In these reports, cisplatin was generally given in combination with other leukemogenic agents.

Gastrointestinal. Marked nausea and vomiting occur in almost all patients treated with cisplatin, and may be so severe that the drug must be discontinued. Nausea and vomiting may begin within 1 to 4 hours after treatment and last up to 24 hours. Various degrees of vomiting, nausea and/or anorexia may persist for up to 1 week after treatment. Delayed nausea and vomiting (begins or persists 24 hours or more after chemotherapy) has occurred in patients attaining complete emetic control on the day of cisplatin therapy. Diarrhea has also been reported.

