18.0 ADVERSE EVENTS

18.1 Adverse Event Characteristics

18.1.1 The AE collection/reporting period will begin with the first day of treatment with metformin and will be completed at 30days following treatment completion. AEs after study registration but prior to the first day of study treatment will be captured as ongoing concurrent secondary diagnoses and symptoms present at the start of study. AEs will be graded in accordance with the NCI Common Terminology Criteria for Adverse Events v4.0 (CTCAE) <http://ctep.cancer.gov/reporting/ctc.html>. If not described in the NCI-CTCAE, AEs will be graded according to their severity using the following criteria: grade 1 (mild), grade 2 (moderate), grade 3 (severe), and grade 4 (life threatening).

18.1.2 This is the attribution scale which will be utilized to attribute relatedness of toxicity to the study:

- Definite – The AE is clearly related to the study treatment.
- Probable – The AE is likely related to the study treatment.
- Possible – The AE may be related to the study treatment.
- Unlikely – The AE is doubtfully related to the study treatment.
- Unrelated – The AE is clearly NOT related to the study treatment.

18.1.3 A definition of expected adverse event and unexpected adverse event:

18.1.3.1 Expected adverse events are those that have been previously identified as resulting from administration of the agent. For purposes of this study, an adverse event is considered expected when it appears in the current adverse event list in the Investigator's Brochure, the package insert, or is included in the informed consent document as a potential risk.

18.1.3.2 An adverse event is considered unexpected when it varies in nature, intensity, or frequency from information provided in

the current adverse event list in the Investigator's Brochure, the package insert or when it is not included in the informed consent document as a potential risk.

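### No blood count or chemistry is scheduled between radiation week 7 and week 17, so transient laboratory toxicity after the last cisplatin doses can go unseen inside the 30-day adverse-event window, and untested patients would count as event-free

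*Combined protocol and SAP*

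**What the plan says.** The study calendar in section 9 gives the blood-test row as "CBC, BMP x x x x x x x x x x x x". Read against the column heads, there are nine marks (pre-study, week -2, weeks 1 to 7), a blank under "30 days post radiation completion", then marks at week 17 ± 2 weeks, year 1 and year 2. Weekly items are "to be completed on day 3 of any given week, +/- 2days". The adverse-event row, "Adverse event evaluation x x x x x x x x x x", starts at week -2 and does include both the 30-day column and week 17. It is the only item marked in the 30-day column.

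Section 9.3.1 allows the 30-day contact to take place by telephone: "A 30 day visit or telephone interview is required for evaluation of Adverse Events". Section 9.3 names no laboratory test. The provision for CBC and BMP at additional visits is in section 9.2.1, which covers evaluation during treatment.

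Section 18.1.1 starts adverse-event collection with the first metformin dose and says it "will be completed at 30days following treatment completion". Sections 6.4, 11 and 12.1.1 also carry toxicity recording to 30 days. Section 18.2.1 requires events of every grade to be recorded, whatever their cause. Sections 12.1.1 and 13.5.1 make all patients evaluable for toxicity from their first metformin dose.

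On cisplatin renal toxicity, section 10.4 says: "It is first noted during the second week after a dose and is manifested by elevations in BUN and creatinine". It adds that this becomes worse with repeated courses. On blood counts it says: "The nadirs in circulating platelets and leukocytes occur between days 18 to 23 (range 7.5 to 45"), with most patients recovered by day 39 (range 13 to 62).

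**The concern.** The plan promises to record toxicity of all grades until 30 days after treatment. A raised creatinine or a low neutrophil or platelet count without symptoms can be found only by a blood test, and none is scheduled between week 7 and the end of that window. A telephone interview cannot find it. Section 10.4 places the expected laboratory effects of the last doses, given when cumulative cisplatin exposure is greatest, in this same stretch of time.

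The protocol summary makes increased systemic toxicity a phase I question. If all treated patients form the denominator and some had no test after week 7, a missing measurement is read as no event. Renal and hematologic rates are then biased downward, in the direction that makes the combination look safer.

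**Working it through.** The plan gives no figure to reproduce. The check is a timeline built from its own dates.

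**Assumptions.** Day 1 is the first radiation day (section 6.1). Radiation starts on a Monday with five fractions a week and no breaks. Cisplatin follows the suggested schedule in section 6.2: weekly from week 1 day 1, up to seven doses. The section 10.4 timing is applied to each dose separately. Calendar weeks are counted from day 1.

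**Fixed dates.**
- Dose k falls on day 7(k - 1) + 1: days 1, 8, 15, 22, 29, 36 and 43.
- Last weekly blood test: 6 × 7 + 3 = day 45, ± 2, so days 43-47.
- End of radiation: 35 fractions end on day 6 × 7 + 5 = 47; 33 fractions end on day 6 × 7 + 3 = 45.
- Adverse-event window closes: 47 + 30 = day 77, or 45 + 30 = day 75.
- Next scheduled blood test: week 15 begins on day 14 × 7 + 1 = 99. The shortest gap is 99 - 47 = 52 days. From nominal day 45 to day 3 of week 17 (16 × 7 + 3 = 115) it is 70 days.

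**Expected laboratory effects by dose.** The second week is taken as dose day + 8 to + 14, and the usual nadir as dose day + 18 to + 23.

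| Dose | Day | Second week (renal onset) | Usual nadir | Position relative to the last test (days 43-47) |
|---|---|---|---|---|
| 4 | 22 | 30-36 | 40-45 | renal onset covered; nadir ends at day 45 |
| 5 | 29 | 37-43 | 47-52 | renal onset covered; nadir after it, except that a day 47 test would meet its first day |
| 6 | 36 | 44-50 | 54-59 | renal onset partly covered; nadir wholly after |
| 7 | 43 | 51-57 | 61-66 | both wholly after |

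For dose 7 the last scheduled test comes only 0 to 4 days after the infusion. Every interval in the dose 5 to 7 rows ends by day 66, before the window closes at day 75-77.

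**What week 17 can show.** Day 99 is 99 - 43 = 56 days after dose 7. Most patients have recovered counts by day 39 after a dose, which is 43 + 39 = day 82 for dose 7. A transient cytopenia will usually have gone. One at the slow end of the stated range (43 + 62 = day 105) might still be visible.

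**Sensitivity to fewer doses.** If cisplatin ends at dose 6, that dose's nadir is still untested and its renal onset is partly tested. If it ends at dose 5, only most of the dose 5 nadir is untested. If it ends at dose 4, the week 7 test lies at or near the end of the usual nadir and the problem largely disappears.

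**The case against.** The strongest reply is that the gap is narrower than it looks and affects no trial decision. Much of that stands.

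- **Testing pauses; it does not end.** Week 17 has both a blood test and an adverse-event evaluation, so persistent toxicity can still be found, although after the section 18.1.1 window has closed. A reader might infer that laboratory monitoring stops at week 7; the calendar does not say so.
- **No scheduled test does not mean no test.** Routine-care or symptom-driven results may exist. The study documentation list in section 14 requires chemistries, hematological parameters and laboratory reports to be kept for all patients. This reduces the problem. It does not remove it, because nothing requires a test to be done in this interval or says how many patients must have one.
- **The plan does not say that an untested patient is recorded as free of toxicity.** That is correct, and no renal or hematologic rate analysis is specified. The point rests on the default: sections 12.1.1 and 13.5.1 make everyone evaluable, with no condition on having been tested.
- **No decision rule is involved.** Section 13.1 limits DLTs to gastrointestinal toxicity and hypoglycemia. A reader might infer that the MTD or dose-escalation decisions are compromised; the documents do not support this.
- **Weekly tests cover most of the exposure**, and the suggested dose is 40 mg/m², while section 10.4 says cytopenias are more pronounced above 50 mg/m². Both limit the likely size.

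A reader might also turn the 28% to 36% renal toxicity in section 10.4 into a number of missed patients. That figure is for a single 50 mg/m² dose. The documents do not support using it as a whole-course rate or sharing it equally over seven weekly doses. Nor would a panel at the 30-day contact necessarily close the gap: day 75-77 is 32 to 34 days after dose 7, past the usual nadir.

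**Conclusion.** The point holds as a limit on the safety description. For at least 52 days no CBC or BMP is scheduled. By the protocol's own timing, that interval contains renal onset after dose 7, the usual nadirs after doses 6 and 7, and most of the dose 5 nadir, all inside the 30-day adverse-event window. Asymptomatic events that resolve before week 17 can be missed. If all treated patients are the denominator, the resulting rates are too low.

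This rests on cisplatin running to week 7 as suggested, and it weakens as fewer doses are given. Treatment breaks or a later end of radiation would move the close of the window later and would not fill the gap. The number of events missed cannot be computed, because the documents give neither an event rate for this regimen nor the extent of routine testing after week 7. The DLT rules, the MTD and the response endpoint are not affected.

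**What to change.** 1. In sections 9.3 and 18: enter into OnCore and grade by CTCAE every CBC and BMP result obtained for any reason between week 7 and the end of the 30-day window. Use the week 17 CBC and BMP to identify persistent toxicity that began in that window.
2. In the safety table: report creatinine, neutrophil and platelet toxicity after week 7 separately, with the number of patients actually tested as denominator, and state that no laboratory test was scheduled in this period.
3. Reconcile the blank 30-day laboratory cell in the calendar and the telephone option in section 9.3.1 with the 30-day toxicity window (sections 6.4, 11, 12.1.1 and 18.1.1) and with the timing in section 10.4. Whether and when to test is for the investigators to decide.

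The cost is a small amount of extra abstraction and some wording changes. Post-week-7 laboratory toxicity rates may come out less favourable, and will be less precise where few patients were tested. Items 1 and 2 use results already in the record and can be applied even after enrollment has ended.

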12.1 Antitumor Effect – Solid Tumors

For the purposes of this study, patients should be reevaluated for response following completion of treatment as per current institutional protocol for this disease site: 1) spiral contrast enhanced computed tomography (CECT) at 8-10 weeks following completion of treatment or 2) positron emission tomography (PET) at 10-12 weeks following completion of treatment. No additional imaging or tests will be performed as part of the current protocol. Following the first post treatment scan, patients will continue routine surveillance using CECT or PET per institutional protocols.

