12.1.5 Duration of Response

Duration of overall response: The duration of overall response is measured from the time measurement criteria are met for CR or PR (whichever is first recorded) until the first date that recurrent or progressive disease is objectively documented (taking as reference for progressive disease the smallest measurements recorded since the treatment started). The duration of overall CR is measured from the time measurement criteria are first met for CR until the first date that recurrent disease is objectively documented. Duration of stable disease: Stable disease is measured from the start of the treatment until the criteria for progression are met, taking as reference the smallest measurements recorded since the treatment started.

12.1.6 Progression-Free Survival: Defined as the duration of time from the date of study registration to the date of documented radiographic progression.

12.1.7 Overall survival: Defined as the duration of time from the date of study registration to the date of the patient’s death due to any cause.

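### After the first response scan, section 9.3.1 makes follow-up imaging depend on suspicion while the study calendar requires it at regular intervals, so later PFS events depend on which passage is followed

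*Combined protocol and SAP*

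**What the plan says.** The endpoint and the imaging that supplies it are described in five places.

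- **Section 12.1.6 (PFS definition):** "Defined as the duration of time from the date of study registration to the date of documented radiographic progression". Imaging is the only source of an event.
- **Section 9.3.1:** clinic visits with laryngopharyngoscopy at 10 weeks after radiation, then every 3 months in year 1 and every 4 months in year 2. Imaging at these visits "is highly recommended if disease progression is suspected by the treating physician". The section then continues: "If performed, radiographic imaging to evaluate the patient for both local-regional recurrence and distant metastases is highly recommended". A visit without a scan therefore complies.
- **Section 9.3.2:** "A chest CT or a PET/CT of chest is recommended once per year".
- **Study calendar (section 9.2, after 9.3.4):** the imaging row and the radiologic evaluation row are both marked at week 17, at the 3-monthly visits of year 1 and at the 4-monthly visits of year 2. Note C to the imaging row reads "Required within 8-12 weeks prior to registration, at end of radiation treatment, and at regular intervals following treatment completion".
- **Section 12.1:** "No additional imaging or tests will be performed as part of the current protocol". The next sentence sends patients to ordinary institutional surveillance by contrast CT or PET and gives no interval.

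Nothing says which passage prevails. Sections 13.4 and 13.5 give no rule for missed or unscheduled scans, for dating progression or for censoring PFS.

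**The concern.** A progression that is not imaged cannot be a PFS event under 12.1.6. Examination and laryngopharyngoscopy can raise suspicion, but they cannot date an event. The blinded radiology review at the end of the study cannot recover scans that were never taken. A patient who seems well at month 9 is scanned under the calendar and need not be scanned under 9.3.1. If that patient has silent disease, the event is dated at month 9 under one passage, and later or never under the other. The Kaplan-Meier PFS curve then reflects local scanning habit as well as the disease. Section 5.1.1 refers to coordinators at each facility, so habits may differ between facilities. Even within one facility, the treating physician's suspicion would decide.

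**Working it through.** The plan states no PFS rate, median, event count or power, so there is no figure to reproduce. The check has two parts.

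**1. Direction, from the passages alone.** The trigger and the obligation differ:

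| Passage | Trigger for a scan after the first response scan | Obligation |
|---|---|---|
| 9.3.1 | Suspected progression | Recommended |
| 9.3.2 (chest) | Once a year | Recommended |
| Calendar and note C | Each marked visit, at regular intervals | Required |
| 12.1 | Institutional routine, no interval | Not a protocol procedure |

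Let T be the true time of progression. Under the calendar, detection is at C, the first visit at or after T. Under 9.3.1, detection is at U, the first visit at or after T at which progression is suspected (or a yearly chest scan shows it). The visits are the same, so U ≥ C for every patient and P(U > t) ≥ P(C > t) at every t. Apparent PFS under 9.3.1 is equal or higher. It is equal only if every progression is picked up at the first visit after it occurs. This step needs no numerical assumption.

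**2. Size, as illustration only.** Visits at 3, 6, 9, 12, 16, 20 and 24 months after radiation come from sections 6.6 and 9.3.1. The rest is assumed: radiation ends 2.1 months after registration, everyone has a first scan 2.3 months later, time to progression is exponential, and a progressed patient not yet detected is scanned at any one visit with probability s.

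A progression with k visits left is missed at all of them with probability (1 − s)^k. At the 24-month visit (26.1 months from registration):

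apparent PFS = true PFS + Σ (1 − s)^k × d_k,

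where d_k is the probability of progressing in the interval that leaves k visits.

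Worked case: true PFS 50% at 24 months from registration, so S(t) = 0.5^(t/24) and S(26.1) = 0.471. For k = 1 to 7, d_k = 0.0576, 0.0647, 0.0726, 0.0602, 0.0657, 0.0716 and 0.0176. With s = 0.5, the terms are 0.0288 + 0.0162 + 0.0091 + 0.0038 + 0.0021 + 0.0011 + 0.0001 = 0.061. Apparent PFS is 0.471 + 0.061 = 0.532. A simulation of 400,000 patients gave 0.531.

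Excess at the 24-month visit, in percentage points:

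| True PFS at 24 months from registration | True value at the reading point | s = 0.75 | s = 0.50 | s = 0.25 |
|---|---|---|---|---|
| 40% | 36.9% | 2.1 | 6.7 | 18.1 |
| 50% | 47.1% | 2.0 | 6.1 | 16.0 |
| 60% | 57.4% | 1.7 | 5.3 | 13.4 |

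Calendar imaging (s = 1) gives the true value at this reading point, so the excess over the calendar is the same. If the yearly chest scan finds every distant failure, assumed to be 35% of progressions, each excess is multiplied by 0.65. The smallest becomes 1.7 × 0.65 = 1.1 points and the largest 18.1 × 0.65 = 11.8.

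A second simulation used a different model: 25-75% of progressions silent, a mean of 4-8 months from progression to symptoms, read at 12 months. With true PFS 63%, the calendar shows 65% and suspicion-triggered imaging 67-74%. With true PFS 50%, the calendar shows 52% and suspicion-triggered imaging 55-64%. The excess over the calendar runs from 67 − 65 = 2 to 64 − 52 = 12 points.

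**The case against.** The case for leaving this alone has several parts.

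- **Section 12.1 implies scanning of well patients.** This stands. Routine surveillance is imaging without suspicion, and 12.1 is compatible with regular intervals. A reader might infer from its sentence on no additional imaging that well patients go unscanned; the next sentence does not support that. The fault in 12.1 is the missing interval. The direct conflict is between 9.3.1 and the calendar.
- **The calendar is loose, not a mandate.** Its rows sit under a heading for collected information, and note C asks for imaging at the end of radiation although no imaging mark appears at week 7 or at 30 days. This weakens note C as a precise rule, but the word required remains, and nothing says that 9.3.1 prevails.
- **PFS decides nothing.** This stands. Section 13.4 calls the secondary analyses exploratory, section 13.1 calls them post hoc, and the phase II rule of 17 responses in 28 uses no later scan. It lowers the priority but does not remove the conflict.
- **Sampling error is larger.** With 28 patients and PFS near 50%, the 95% half-width is 1.96 × √(0.25/28) = 0.185, about 18.5 points if censoring is ignored. That is right, but the delay always acts in one direction and a confidence interval does not show it.
- **Scheduled scans also date progression late.** This is true, by up to one interval, and it is why the working compares the 9.3.1 rule with the calendar.

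**Conclusion.** The conflict is in the current text and should be resolved. For progressions after the first response scan, the PFS date depends on which passage is followed. Following 9.3.1 can only leave apparent PFS equal to, or higher than, what the calendar would give.

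The size cannot be derived from the documents. The range from about 1-2 to 12-18 points rests on assumed progression rates, detection probabilities and symptom delays. Regular examination and yearly chest imaging pull it towards the lower end.

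Two stronger readings are tempting and not supported. One is that every PFS event is affected: the scan at 8-12 weeks can itself show progression and supply an event, and it lies outside this conflict. The other is that PFS would be inflated against historical controls: sections 1.0 and 2.1 tie that comparison to disease response, no comparator is named for PFS, and the documents do not say how the controls were imaged.

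The primary response endpoint is unaffected. Priority is minor to moderate.

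**What to change.** Reconcile 9.3.1, 9.3.2, 12.1 and note C into one stated follow-up imaging schedule for dating PFS, and add to section 13.4 that patients without progression are censored at the last adequate scan. The sponsor has two ways to do this:

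- **If the calendar governs:** state in 9.3.1 that imaging at the marked visits does not depend on suspicion, and bring 12.1 into line.
- **If suspicion-triggered imaging is intended:** correct the calendar marks and note C. Report the endpoint as clinically triggered radiographic progression, with the caveat that it may be higher than PFS from scheduled imaging.

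Either way the change is to protocol wording. The first option has a small downside: if 9.3.1 reflects current practice, more scans would be done than now, although none beyond those the calendar already marks. The second adds no scans but limits what the PFS curve can be used for.
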